6.5.1. Analysis Methods

The VEs will be calculated for the above endpoints, occurring during the first year, during the second year and over the whole study, except for all endpoints related to RT-PCR confirmed influenza-mediated ARI and LRTD. For all exploratory endpoints related to influenza-mediated ARI and LRTD only the proportion of participants meeting the respective endpoints, will be summarized.

The PPE set will be used for the analysis of these exploratory endpoints.

For endpoints focusing on the first year or during the whole study, events with onset at least 14 days after the vaccination will be considered. And for endpoints focusing on the second year, event with onset from the study Day 365 onwards will be considered.

A similar Exact Poisson regression model as for the primary and secondary endpoints will be used and exact 2-sided 95% CIs for VE (1-relative risk rate) will be calculated. For endpoints focusing on the whole study or the second year, the follow-up time is determined in a similar way as for the primary and secondary endpoints, respectively. For endpoints focusing on the first year, the follow up time is defined as the time between 14 days post vaccination (vaccination day + 14 days) and occurrence of the first event during the first year; for participants with no events, it is the time between 14 days post vaccination and the minimum of the database cut-off date of the analysis and a day prior to study Day 365 (or relative day 365, if the Day 365 visit not available but there are ARI surveillance questions available after the relative day 365). However, for participants who discontinued the study before having an event, follow-up time is defined as the time between 14 days post vaccination and the minimum of the database cut-off date, a day prior to study Day 365 (or relative day 365, if the Day 365 visit not available but there are ARI surveillance questions available after the relative day 365) and date of last contact (day of discontinuation).

The proportion of participants meeting the different exploratory endpoints, will also be summarized with the corresponding VE and will be depicted with forest plots.

The proportion of participants with emerging therapeutic interventions of interest by subcategory (bronchodilator/nebulizer treatment, corticosteroid prescription, antibiotic prescription, antiviral prescription) associated with RT-PCR-confirmed RSV-mediated ARI, LRTD and no LRTDs will also be summarized per group, category and risk level, for the first, second year and over the whole study. In case a participant had multiple RT-PCR confirmed RSV-mediated ARIs or LRTDs during the reported period, then the therapeutic interventions corresponding with the first occurrence of RT-PCR confirmed RSV-mediated ARI or LRTD will be used, respectively.

The proportion of participants with therapeutic interventions of interest by subcategory at the days of vaccination will also be summarized per group, category and risk level.

6.6. Other Exploratory Analysis

If the primary analysis occurs in 2022 the exploratory endpoints related to the whole study (data collected up to Data base cut off) will be analyzed, and the first- and second-year endpoints will not be analyzed at that timepoint.

If the primary analysis occurs in 2023 all exploratory endpoints will be analyzed up to the date of the data base cut off.

6.6.1. ARI Duration

For participants with an RT-PCR confirmed RSV-mediated ARI and for those with a RT-PCR-confirmed RSV-mediated LRTD, the ARI duration will also be summarized with Kaplan Meier curves. The duration is defined as: end date of the ARI episode – start date of the ARI episode + 1 (see section 6.3.1). Hazard ratios will be calculated, with a Cox proportional hazard model with ARI duration as dependent variable and group as independent variable for the whole study. In case that the ARI was stopped by the PI before the two consecutive days back to baseline for the RiiQ assessment (indicated by a flag in the DB), the record will be considered to be censored.

Similar to the ARI duration, the **time to first occurrence** for a RT-PCR confirmed RSV-mediated ARI, LRTD, ARI by subtype and LRTD by subtype will be summarized with Kaplan Meier curves. Hazard ratios will be calculated, with a Cox proportional hazard model with time to first occurrence as dependent variable and group as independent variable for the first year, second year and the whole study. Participants with no events will be considered in the analysis as censored records.

Time to first occurrence, will be calculated for:

- first and second year separately, (determination of the time to first occurrence is similar to ‘follow up time’ as described in Section 6.4.1.2.1 and 6.5.16.3.3)
- the entire study (determination of the time to first occurrence is similar to ‘follow up time’ as described in Section 6.3.3 and 6.4.1.2.1)

In case a participant had multiple RT-PCR confirmed RSV-mediated ARIs or LRTDs during the reported period, then the first occurrence of RT-PCR confirmed RSV-mediated ARI or LRTD will be used, respectively.

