Participants with positive RT-PCR results for RSV (or hMPV or influenza) should keep on filling out the daily ARI episode questionnaires until resolution of the ARI episode independently of any other co-infection (including SARS-CoV-2).

Further Procedures for Participants with an RSV, hMPV, or Influenza-mediated ARI^a

- Continue completing the RiiQ ([Appendix 8](#)) until resolution* of the ARI episode in the eDiary every evening (preferably).
- Continue completing the following scales until resolution* of the ARI episode:
 - EuroQoL, 5-Dimension, 5-Level (EQ-5D-5L) ([Appendix 9](#)),
 - Patient Global Impression of Health (PGI-H) scale,
 - Patient Global Impression of Severity (PGI-S) scale,
 - Patient Global Impression of Change (PGI-C) scale, and
 - Return to Usual Health question ([Appendix 10](#)).

* A resolved ARI episode is defined as 2 consecutive days with no symptoms listed on the RiiQ Symptom Scale, or, for participants who have RiiQ symptoms at baseline (assessed pre-vaccination), 2 consecutive days where all symptoms on the RiiQ Symptom Scale have returned to the same severity level as reported at baseline (or lower). After resolution of the ARI episode, the participant will return to ARI surveillance with twice weekly reminders.

- On ARI Day 29 (± 7 days), participants will be asked to return to the site if a sputum sample was provided by the participant at ARI Day 3-5 visit, regardless of the swab RT-PCR test results, AND/OR at least one of the nasal swab samples collected could not be tested at the study site with the BioFire Filmarray Respiratory panel (RT-PCR test) and had to be shipped for central laboratory test AND/OR at least one nasal swab sample had a positive RT-PCR result for either RSV, hMPV, or influenza when tested at the study site. The ARI Day 29 visit can take place by telephone or telemedicine contact. During this visit:
 - The MRU questionnaire will be completed ([Appendix 11](#)) based on interview with the participant.
 - Participants will complete the RiiQ ([Appendix 8](#)), the EQ-5D-5L ([Appendix 9](#)) and each of the PGI scales and the Return to Usual Health question ([Appendix 10](#)) on the participant's eDiary.
 - The site staff will also collect information on days missed from work ([Appendix 12](#)) and on complications, hospitalizations and concomitant medications related to the ARI and record in the eCRF.

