5. PLANNED ANALYSIS

5.1. Analysis Plan for the Interim and Primary Analysis

Figure 1 displays the interim and primary analysis plan.

Figure 1: Interim and Primary Analysis Plan

For the first interim analysis, ARIs with an onset up to 1 September 2022 will be included and a database cut-off of 15 September 2022 will be used. For the second IA, ARIs with an onset up to 10 October 2022 will be included and a database cut-off of 24 October 2022 will be used. For the third IA, ARIs with an onset up to 8 January 2023 will be included and a database cut-off of 22 January 2023 will be used. For the primary analysis, ARIs with an onset up to 15 April 2023 will be included and a database cut-off of 30 April 2023 will be used.

DB= database, IA= interim analysis, IDMC = independent data monitoring committee, PA=primary analysis, PPE=Per-protocol Efficacy, POS= positive

Please refer to Section 9.5.1 in the CTP for more details on the timing of the Interim and Primary analysis. Information regarding additional country-specific enrollment, beyond the global cohort enrollment, can be found in the country specific amendments.

In case the analysis is conducted prior to the completion of the study recruitment, all participants recruited in the global and local cohorts up to the database cut off will be used in the efficacy analysis, regardless the number of events already observed in the different local cohorts. Moreover, only participants vaccinated >14 days prior to the database cut off will be taken into account for the analysis of the primary efficacy endpoint, including the counting of LRTD cases. For the sensitivity analysis based on the FAS all participants will be taken into account.

Note: Participants with an RT-PCR-confirmed RSV-mediated ARI with onset within 14 days after vaccination, participants who discontinue within 14 days after vaccination and participants that have not reached 14 days (inclusive) after vaccination, will be excluded from the PPE population and thus from the counting of the number of events.

Local study teams will be blinded to study vaccination until the primary analysis as specified per local requirements. The local cohorts' primary analysis cannot be conducted prior to the primary analysis of the global cohort.

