6.3.1. Definition of Endpoint

A participant will be considered to have RT-PCR-confirmed RSV-mediated LRTD if the following criteria are met:

- New onset or worsening from baseline of 3 or more of the below symptoms as captured in the RiiQ at the same assessment time point:
 - Cough
 - Short of breath
 - Coughing up phlegm (sputum)
 - Wheezing
- AND
- Confirmation of RSV by RT-PCR in one or more of the nasal swabs, or in the sputum sample (when available)

Prior to database lock for all planned analyses, the CEC will review all available data of all RT-PCR confirmed RSV-mediated ARIs and will confirm if the above criteria are met. If the CEC confirms that the criteria for RT-PCR-confirmed RSV-mediated LRTD are met, the cases will be counted as a primary endpoint in the statistical analysis. This will be done in two steps:

Step 1:

The set of RT-PCR confirmed RSV-mediated ARIs for which the CEC will review all available data will be determined programmatically as follows:

ARI episode definition

An ARI episode is defined as an episode reported by the participant and confirmed by the site, which is captured on the ‘Acute Respiratory Infection’ form of the CRF, meaning that all ARIs with a confirmed start (CESTDTC) and end (CEENDTC) date on this form will be considered an ARI episode. ARIs initiated by error and their respective symptoms will be removed from the analysis.

Note: In the cases that an RSV ARI is ongoing during the DB cut off, the database cutoff date will be used as an interim ARI end date for the purposes of the analysis. An ARI with no end date will be considered as an RSV ARI, if an RSV positive result is available within 15 days after the ARI onset.

ARI episode duration

The duration of an ARI episode is defined based on the ARI start and ARI end date reported in the CRF: *end date of ARI - start date of ARI + 1 (CEENDTC - CESTDTC + 1)*.

RSV RT-PCR Confirmation of the Considered ARI Episode

Confirmation of RSV infection by RT-PCR for the primary endpoint will be done in nasal swabs or sputum samples.

For samples collected outside of China, a sample is considered RSV positive if:

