6.11. Discontinuation of the study

On the 29th of March 2023 the EVERGREEN study was permanently terminated. All participants are to be followed up for 6 months post vaccinations for safety collection. ARIs will not be collected after the 29th of March 2023 or followed up.

Due to the early termination of the study, the Sponsor decided not to perform the complete planned analysis as described in the protocol and SAP. The final analysis will contain the following:

- Efficacy analysis for secondary endpoints and for a limited selection of the exploratory endpoints.
- Safety analysis presented only per period (as defined in [Table 4](#)).
- Immunogenicity analysis of all completed assays in the database at the time of the analysis.

Moreover, no local specific cohort analysis will be conducted.

The following efficacy endpoints will be analyzed per year and over the whole study:

- First occurrence of any RT-PCR-confirmed RSV-mediated LRTD and ARI
- First occurrence of any RT-PCR-confirmed RSV-mediated LRTD and ARI by subtype
- First occurrence of any clinically relevant diseases associated with RT-PCR-confirmed RSV-mediated LRTD and ARI
- AUC for participants with any RT-PCR-confirmed RSV-mediated LRTD and ARI
- Viral loads

Note: In the cases that an RSV ARI is ongoing during the time of the discontinuation and does not have an end date, the 29th of March 2023 will be used as an ARI end date. An ARI with no end date will be considered as an RSV ARI, if an RSV positive result is available within 15 days after the ARI onset.

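### SAP 6.6.1 has no censoring rule for RSV ARIs still ongoing at the data cut-off, so as written they count as resolved that day: duration is understated and the hazard ratio can be biased in either direction

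*SAP*

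**What the plan says.** **Duration and model.** SAP 6.6.1 defines duration as ARI end minus ARI start plus one day, referring to 6.3.1. It is analysed in participants with RSV-mediated ARI and in those with RSV-mediated LRTD, by Kaplan-Meier and a "Cox proportional hazard model with ARI duration as dependent variable and group as independent variable for the whole study".

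**Censoring.** 6.6.1 gives one rule for duration: a record is censored when its episode had been "stopped by the PI before the two consecutive days back to baseline for the RiiQ assessment (indicated by a flag in the DB".

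**End date of an ongoing episode.** SAP 6.3.1: if an RSV ARI is ongoing at cut-off, "the database cutoff date will be used as an interim ARI end date for the purposes of the analysis". SAP 6.11, written after termination, says that for episodes without an end date "the 29th of March 2023 will be used as an ARI end date".

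**Resolution.** Protocol 8.1: "A resolved ARI episode is defined as 2 consecutive days with no symptoms listed on the RiiQ Symptom Scale", or two consecutive days back at the baseline level or lower for participants with baseline symptoms.

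**Gap from last eligible onset to cut-off.** SAP 5.1 on the third interim reads: "ARIs with an onset up to 8 January 2023 will be included and a database cut-off of 22 January 2023 will be used". On the primary analysis it reads: "ARIs with an onset up to 15 April 2023 will be included and a database cut-off of 30 April 2023 will be used".

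**The concern.** In a time-to-resolution analysis, the data cut-off is a reason to stop observing, not an outcome. An ill participant should contribute follow-up to that date and then be censored. Applied literally, 6.6.1 and 6.3.1 together turn the cut-off into a recovery.

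The SAP's other wording does not rescue this. Section 6.6.9 uses censored as a synonym for closed by the PI, which suggests that PI closure is the only censoring the authors had in mind for episodes. The same section calls the cut-off a temporary end date, so they knew it was not a resolution. Where other censoring is meant, it is stated: time to first occurrence in 6.6.1, and 6.6.7.2, which censors a participant who has not returned to usual health at the last reply. Two recovery measures on the same episodes thus treat unresolved illness differently.

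At stake is the reported length of RSV illness and the between-arm comparison of it. The affected episodes are those that started late or ran long. Protocol 8.1 plans for episodes still ongoing at the ARI Day 29 visit, so illnesses longer than the gap are expected.

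**Working it through.** The documents give no duration distribution, count of ongoing episodes or target hazard ratio for this analysis, so there is no plan figure to reproduce. The day count is confirmed by the SAP's own example in 6.6.9: 10 to 23 August 2022 gives 23 − 10 + 1 = 14 days.

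**Step 1: which episodes can be affected.** The gap is 14 days at the third interim (8 to 22 January) and 15 days at the primary analysis (15 to 30 April). An episode with onset on the last eligible day and still open at cut-off is recorded as 22 − 8 + 1 = 15 days, or 30 − 15 + 1 = 16 days. Shorter recorded durations are not imputed at these cut-offs. For 29 March 2023 no gap is stated.

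**Step 2: share still open.** Assume exponential durations with mean m, a gap of 14 days and onsets spread evenly over W days. Then q = (m/W) × [exp(−14/m) − exp(−(14+W)/m)].

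| m (days) | q, W = 90 | q, W = 365 |
|---|---|---|
| 10 | 2.7% | 0.7% |
| 14 | 5.7% | 1.4% |
| 21 | 11.8% | 3.0% |
| 28 | 18.1% | 4.7% |

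The onset window matters as much as the illness length, and neither is known.

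**Step 3: direction of the bias.** Under the same model the mean recorded duration is m(1 − q). If every record is an event, the resolution rate is 1/[m(1 − q)], so

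ratio as written = true ratio × (1 − q_placebo)/(1 − q_vaccine).

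- Same onset calendar, means 21 (placebo) and 14 (vaccine), W = 90: 1.5 × (1 − 0.118)/(1 − 0.057) = 1.40. The ratio moves toward 1.
- If more vaccine-arm episodes are open at cut-off, the factor exceeds 1. With no true difference and 7.2% (placebo) against 12.9% (vaccine) open: 0.928/0.871 = 1.07, an apparent benefit from none.

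**Step 4: Cox model.** Simulation with assumed inputs: Weibull durations with shape 1.5, equal case numbers per arm, 30,000 cases per scenario. A hazard ratio above 1 means faster resolution on vaccine. Selected rows, all with a 60-day onset window:

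| Onset timing | True HR | Placebo median (d) | Gap (d) | Open, placebo / vaccine | HR censored | HR as written |
|---|---|---|---|---|---|---|
| Same in both arms | 1.3 | 14 | 15 | 7.9% / 4.8% | 1.295 | 1.271 |
| Same | 1.3 | 21 | 15 | 18.7% / 13.4% | 1.289 | 1.235 |
| Same | 1.3 | 21 | 0 | 38.6% / 32.8% | 1.319 | 1.204 |
| Vaccine later | 1.0 | 14 | 15 | 7.2% / 12.9% | 0.993 | 1.072 |
| Vaccine later | 1.0 | 21 | 0 | 39.5% / 56.4% | 0.995 | 1.382 |
| Vaccine later | 1.3 | 21 | 15 | 18.5% / 20.8% | 1.309 | 1.424 |

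Over placebo medians of 10, 14 and 21 days and onset windows of 60 and 180 days:

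- Same calendar, true 1.3: 1.24 to 1.30 with the 15-day gap and 1.20 to 1.27 with none; 1.27 to 1.32 when censored.
- Vaccine-arm onsets later: true 1.0 becomes 1.02 to 1.38, and true 1.3 becomes 1.30 to 1.58 (1.28 to 1.33 when censored).
- The placebo median falls by 0 to 2 days with the 15-day gap and by 0 to 7 days with none.

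**The case against.** **No sentence says these episodes are events.** The date is called interim, and a programmer might censor it unprompted. That is fair as a prediction, but the text lists one censoring rule and these records do not meet its description. A plan should not depend on the programmer departing from it.

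**A reader might infer that the rule always shrinks the vaccine's benefit.** The documents do not support that. It needs a similar spread of onsets relative to cut-off in both arms. The cases arise after randomisation and second-year efficacy is itself a study question, so later onsets in the vaccine arm are possible and reverse the bias.

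**A reader might infer that a fatal episode, or one cut short by withdrawal, counts as a quick recovery.** This is not shown. Sites can end episodes manually (protocol 8.1), and an episode closed by the site before return to baseline could fall under the existing PI-stopped rule. The SAP is silent, which is a gap to close rather than a demonstrated miscount.

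**A reader might infer that the 29 March 2023 date distorts the final analysis of duration.** SAP 6.11 lists the efficacy endpoints retained, and ARI duration is not among them.

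**Stakes are low.** This stands. Duration is under other exploratory analyses and is not a protocol endpoint. The recovery endpoint in the protocol, time to return to usual health, already censors. The primary endpoint takes its event time from the ARI start (SAP 6.3.3).

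**Conclusion.** The point holds as a missing censoring rule. Followed literally, 6.6.1 and 6.3.1 record an RSV ARI that is open at cut-off as resolved on that date. Duration for those episodes cannot be overstated and is understated whenever the illness continues. The sign of the bias in the hazard ratio is not determined by the documents.

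The effect is probably small at the planned cut-offs, where the 14- to 15-day gap protects most episodes. Sampling error is likely to be larger. For the LRTD analysis, with the target of 76 events and, at best, an even split, the standard error of the log hazard ratio is about √(1/38 + 1/38) = 0.23, against ln(1.30/1.24) = 0.05 for the low end of the same-calendar range. The bias grows if illnesses are long, if onsets bunch before cut-off, or if 29 March 2023 is ever used to compute duration. In practice it bears on any analysis that reports ARI duration outside the reduced final set. All sizes rest on assumed durations and onset patterns.

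**What to change.** In SAP 6.6.1:

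1. State that the event is documented resolution as defined in protocol 8.1.
2. State that an RSV ARI whose end date is imputed (database cut-off or 29 March 2023), or that ends without documented resolution, is censored. Choose either that date or the last RiiQ assessment, and use it throughout.
3. Say explicitly how episodes ended by death or withdrawal are classified, since the present text leaves this open.

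Keep the imputed end dates in 6.3.1 and 6.11 for their other uses. Case ascertainment, the AUC window (6.4.2, with AUC retained in 6.11) and RiiQ compliance (6.6.10) all need an end date.

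The cost is a few sentences and one censoring flag in the analysis dataset. No new data are needed. If duration has already been reported, give the number of episodes per arm with an imputed end date and rerun the model with them censored.

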6.6.2. ARI Symptoms

For participants with RT-PCR-confirmed RSV-mediated ARIs, influenza-mediated ARIs and hMPV-mediated ARIs the combination of the symptoms (cough, short of breath, coughing up phlegm ,wheezing, fever and fatigue) will be summarized per group and risk level for each year separately and over the whole study.

6.6.3. ARI Complications

All complications associated with any RT-PCR confirmed RSV-mediated ARI, LRTD, and non LRTD will be summarized per group and per risk level, during the first and the second year separately, and over the whole study. A summary table including the number of participants with

any complication, any complication per worst grade reported, with fatal outcome and reported as SAE will be created. All complications and those reported as SAEs will also be summarized by System Organ Class and Preferred Term. In case a participant had multiple RT-PCR confirmed RSV-mediated ARIs or LRTDs during the reported period, then the first occurrence of RT-PCR confirmed RSV-mediated ARI or LRTD will be used, respectively.

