9.4.3. Safety Analyses

No formal statistical testing of safety data is planned. Safety data by vaccination group and based on the FAS will be analyzed descriptively. The analysis of solicited and unsolicited AEs will be restricted to a subset of the FAS (ie, the Safety Subset). For the analyses of AESIs, SAEs, and COVID-related AEs, the entire FAS population will be used.

The impact of baseline factors (such as being at increased risk for severe RSV disease) may be explored as well.

Adverse Events (Solicited and Unsolicited)

Solicited local (at injection site) and systemic AEs will be summarized descriptively. Solicited AEs shown in the tables and listings will be based on the overall assessment of the investigator. The overall frequencies by vaccine group as well as the frequencies according to severity and duration will be described for solicited AEs. The number and percentages of participants with at least one solicited local (at the injection site) or systemic AE will be presented. Frequencies of unsolicited AEs, separately for all and vaccination-related only, will be shown by system organ class and preferred term, while those of solicited AEs will be presented only by preferred term.

The verbatim terms used in the eCRF by investigators to identify AEs will be coded using the Medical Dictionary for Regulatory Activities (MedDRA). Reported AEs with onset during the active vaccination phase (ie, AEs occurring post vaccination up to 28 days post-vaccination) and SAEs and AESIs will be included in the analysis. For each AE, the number and percentage of participants who experience at least one occurrence of the given event will be summarized by group.

Summaries, listings, datasets, or participant narratives may be provided, as appropriate, for those participants who die, who discontinue the study (or vaccination, if applicable) due to an AE, or who experience a severe AE or AESI or SAE or COVID-19 infection.

ARIs recorded as (S)AEs in the eCRF will be excluded from any (S)AE analysis if the laboratory RT-PCR is subsequently found to be positive for RSV. ARIs arising from RSV infection will not be reported as (S)AEs in the Clinical Study Report, as they are endpoints of the study and will be tabulated separately.

Vital Signs

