6.4.1. Key Confirmatory Secondary Endpoints

The following secondary endpoint will be formally analyzed:

1. First occurrence of any RT-PCR-confirmed RSV ARI, with onset at least 14 days after dosing of study vaccine
2. First occurrence of any RT-PCR-confirmed RSV-mediated LRTD during the second year, with onset after study Day 365
3. First occurrence of any RT-PCR-confirmed RSV ARI during the second year, with onset after study Day 365
4. First occurrence of predefined clinically relevant disease associated with RT-PCR-confirmed RSV-mediated ARI over the whole study, with onset at least 14 days after dosing of study vaccine

Formal inference for secondary endpoint 1 (RSV ARI) as part of the testing strategy will occur at the primary analysis, for secondary endpoints 2, 3 and 4 the formal inference as part of the testing strategy will only occur at study end (Table 10). Exploratory descriptive analyses of these endpoints might also occur at other planned analysis timepoints.

Note: Occurrence is always referring to the start of the ARI as reported in the CRF (CESTDTC). Second year starts at the study Day 365 visit, or relative day 365, in case Day 365 visit not available but there are ARI surveillance questions available after the relative day 365.

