6.6.4. Clinically Relevant Disease

The proportion of participants with clinically relevant disease (See Section 6.4.1) by subcategory associated with RT-PCR-confirmed RSV-mediated ARI, LRTD and non LRTD will also be summarized per group, category and risk level for the first and second year separately and over the whole study. In case a participant had multiple RT-PCR confirmed RSV-mediated ARIs or LRTDs during the reported period, then the first occurrence of RT-PCR confirmed RSV-mediated ARI or LRTD will be used, respectively.

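### Whole-study RSV ARI tables of complications, clinically relevant disease and interventions use only each participant's first RSV ARI, so an outcome counted in year 2 can be missing from the whole-study table (a small, descriptive effect)

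*SAP*

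**What the plan says.** SAP 6.6.3 opens broadly: "All complications associated with any RT-PCR confirmed RSV-mediated ARI, LRTD, and non LRTD will be summarized per group and per risk level", for the first year, the second year and the whole study. Its rows count participants: "any complication per worst grade reported, with fatal outcome and reported as SAE will be created". The section ends with a restriction: "In case a participant had multiple RT-PCR confirmed RSV-mediated ARIs or LRTDs during the reported period, then the first occurrence" of the RSV ARI or LRTD is the one used, respectively. So the ARI tables use the first ARI and the LRTD tables use the first LRTD. How the rule works for the non-LRTD tables is not stated.

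Two other sections carry the same rule over the same three periods:

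- SAP 6.6.4: "The proportion of participants with clinically relevant disease (See Section 6.4.1) by subcategory associated with RT-PCR-confirmed RSV-mediated ARI", and likewise for LRTD and non-LRTD.
- SAP 6.5.1, for emerging interventions: "then the therapeutic interventions corresponding with the first occurrence of RT-PCR confirmed RSV-mediated ARI or LRTD will be used".

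The efficacy endpoints are defined differently. Confirmatory endpoint #4 in SAP 6.4.1 is "First occurrence of predefined clinically relevant disease associated with RT-PCR-confirmed RSV-mediated ARI over the whole study". The exploratory endpoints in SAP 6.5 for complications, hospitalisation, pneumonia and interventions also take the first occurrence of the outcome, not the first ARI.

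Protocol 9.4.3 keeps RSV ARIs out of the (S)AE reporting "as they are endpoints of the study and will be tabulated separately".

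**The concern.** Within 6.6.3, the opening promise to cover any RSV ARI conflicts with a closing rule that keeps one episode per participant. The rule suits quantities measured once per episode. It does not suit rows that ask whether something ever happened, or how bad it was at worst.

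Because first is judged within each period, the periods do not nest. A second RSV ARI can be the first of year 2 and so appear in the year-2 table, yet be absent from the whole-study table. A whole-study count can then be too low and, in a sparse row, lower than the count for one of its own years. The same participant can be an endpoint #4 event and appear under no subcategory in the whole-study ARI breakdown of that endpoint.

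**Working it through.** The documents give no figure on this point, so there is nothing to reproduce. The check has two parts.

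**1. The counting rule.** Allow at most one RSV ARI per year, each either complicated or uncomplicated, which gives nine participant types. Four types have no complicated episode and count zero everywhere. The other five, in the ARI tables:

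| Year 1 ARI | Year 2 ARI | Year 1 count | Year 2 count | Whole study, SAP rule | Whole study, any episode |
|---|---|---|---|---|---|
| none | complicated | 0 | 1 | 1 | 1 |
| uncomplicated | complicated | 0 | 1 | **0** | 1 |
| complicated | none | 1 | 0 | 1 | 1 |
| complicated | uncomplicated | 1 | 0 | 1 | 1 |
| complicated | complicated | 1 | 1 | 1 | 1 |

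Only the second row is miscounted. From the table, whole study minus year 2 = (complicated in year 1 and not in year 2) − (uncomplicated in year 1, complicated in year 2). The whole-study count falls below year 2 when the second group is the larger.

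Example: two participants uncomplicated then complicated, one complicated in year 1 only, three complicated in year 2 only. Year 1 = 1. Year 2 = 2 + 3 = 5. Whole study under the SAP rule = 1 + 3 = 4. Under any-episode counting it is 2 + 1 + 3 = 6. In a rare row one case is enough: no fatal outcome in year 1 and one fatal second episode in year 2 gives year 2 = 1 and whole study = 0.

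**2. The size.** Inputs:

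- 7,670 placebo and 15,340 active participants (Protocol 9.2.1).
- Yearly attack rate *a* = 2.4%, the infection rate quoted in Protocol 2.2 from a Japanese cohort aged 65 and over, with an assumed range of 1% to 5%.
- VE of 65% against ARI. This is an assumption: the protocol's 65% is for LRTD.
- 10% loss before year 2, and independence between years (assumed).
- Probability *q* that an RSV ARI has the outcome of a given row: 0.2% to 20% (assumed).

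Participants with an RSV ARI in both years = N × *a*² × 0.9, with *a* multiplied by 0.35 in the active group. At 2.4%:

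- Placebo: 7,670 × 0.024² × 0.9 = 3.98.
- Active: 15,340 × (0.024 × 0.35)² × 0.9 = 0.97.

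Expected dropped episodes = that number × *q* × (1 − *q*). For placebo at 2.4%, this is 3.98 × 0.002 × 0.998 = 0.008 up to 3.98 × 0.2 × 0.8 = 0.64.

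| Attack rate | Placebo, both years | Placebo, dropped | Active, both years | Active, dropped |
|---|---|---|---|---|
| 1% | 0.69 | 0.001 to 0.11 | 0.17 | under 0.001 to 0.03 |
| 2.4% | 3.98 | 0.008 to 0.64 | 0.97 | 0.002 to 0.16 |
| 5% | 17.26 | 0.03 to 2.8 | 4.23 | 0.008 to 0.68 |

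With Poisson counts, the chance that a given cell has a whole-study count below its year-2 count is at most about 1.6% (placebo, 5% attack rate, *q* = 0.2%). It is close to zero for common outcomes.

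For the LRTD tables the earlier episode must itself be an LRTD. At the protocol's placebo incidences of 0.2% and 0.5%, 7,670 × 0.002 × 0.005 × 0.9 = 0.07 participants would have an LRTD in both years.

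This check covers one episode per year only. A second episode within the same year is dropped from that year's table too. SAP 6.3.1 allows one sample to be attributed to two ARIs when the second starts within 7 days of the first, so a single infection could be recorded as two RSV ARIs. The documents give no frequency for this.

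**The case against.** The strongest reply is that little depends on these tables. SAP 6.5 and 6.5.1 already plan outcome-based proportions and VE, by year and over the whole study, for complications, hospitalisation, pneumonia, interventions and clinically relevant disease. What the rule affects is the detail: worst grade, fatal, SAE, system organ class and preferred term, and subcategory. SAP 6.11 ended ARI collection on 29 March 2023 and cut the final analysis. It keeps clinically relevant disease as a first-occurrence endpoint but does not list the complication or intervention tables. All of this stands, and it limits the point. It does not remove the contradiction inside 6.6.3.

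Four stronger readings are tempting, and the documents do not support them:

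- *A fatal or serious complication of a second episode disappears from the report.* Protocol 9.4.3 and SAP 6.7.1.1.1 exclude the ARI recorded as an (S)AE. They do not say that a complication reported as its own SAE is excluded, and Protocol 8.4 names ARIs and complications separately. SAP 6.7.1.1.2 plans fatal-SAE tables, and listings or narratives as appropriate. How well this route covers year 2 depends on the reporting window for these SAEs, which is 24 months in Protocol 8.4 but 6 months in footnote l of Protocol 1.3.2. Those passages must be reconciled.
- *Every participant with two RSV ARIs is miscounted.* Only those with an uncomplicated first and a complicated second episode are.
- *The subcategories should add up to endpoint #4.* One participant can meet several subcategories, so they do not sum to it under any rule. The fault is a missing participant.
- *A severe second episode is always lost.* If it is the participant's first LRTD, it stays in the LRTD tables.

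**Conclusion.** The point holds as an internal inconsistency that gives a wrong whole-study count in the ARI tables of SAP 6.6.3, 6.6.4 and 6.5.1. It is confined to descriptive tables: endpoint #4 and the exploratory VE endpoints count the outcome itself, so no confirmatory result changes.

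The expected effect is small. At a 2.4% attack rate well under one complicated episode would be dropped in placebo, and fewer in the active group. Only at 5% with a common outcome does the expectation exceed one, and there a single participant hardly alters the row. The effect matters in sparse rows: fatal, SAE and single preferred terms. These sizes rest on an infection rate from one cohort, an assumed VE against ARI, independence between years and a full second year; the early stop of ARI collection would lower them. The case for changing the rule is the contradiction and the low cost of removing it, not the number of participants.

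**What to change.** Wherever these tables are produced, replace the first-episode rule in SAP 6.5.1, 6.6.3 and 6.6.4 for yes/no and worst-grade outcomes. Count the participant if the outcome occurred in any RSV ARI (or any RSV LRTD, for the LRTD tables) in the reported period, and take the worst value across episodes. State how this applies to the non-LRTD tables. Whole-study counts will then be at least as large as those of either year. At minimum, keep the existing tables and add any-episode rows for fatal outcome, SAE and worst grade.

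Apply the same rule to the yes/no medical resource counts in SAP 6.6.8, which use the first episode too. Keep the first episode for AUC, viral load and ARI Day 3-5 vital signs, and label those tables *first RSV episode only*.

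The cost is a sentence in each section and a small programming change, with no new data. The downside is that any-episode counts will differ from the tables that stay first-episode. For example, low oxygen saturation, tachypnea and hypotension in 6.6.4 may not match the vital signs in 6.6.5. The labels explain why.
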